- Fasting blood Insulin
- Adiponectin

Patients who are discontinued early from the study will complete the EOS evaluations at the time of early discontinuation.

Unscheduled visit

The patient may be required to return for an unscheduled visit for a repeat measurement of fasting blood glucose, if the investigator deems it necessary.

² HOMA = The Homeostasis Model Assessment

Self-Monitoring Fasting Blood Glucose and Patient Diaries

All patients will self-monitor fasting morning blood glucose levels three (3) times weekly during the run-in and treatment period. Monitoring must be performed at the same time each designated day (\pm 10 minutes) prior any caloric intake. Patients will be required to record the values in a patient diary and bring the diary to each clinic visit; Information recorded for the fasting blood glucose will be reviewed by the clinical research coordinator for completeness and transcribed onto CRF's. During the study, both fasting finger stick glucose and laboratory fasting plasma glucose will be obtained.

If a fasting blood glucose measures greater than or equal to 270 mg/dL (15 mmol/L) during daily self-monitoring or during any in-clinic visit, the patient will be required to contact the clinic to report the value. Blood will be drawn and sent to lab for plasma glucose determination. The patient may be required to return for an unscheduled visit to the clinic for a repeat measurement of fasting blood glucose within one week after the original measurement. If the repeat measurement is also greater than or equal to 270 mg/dL, the patient will be discontinued from treatment with study drug and offered rescue medication. The patient will continue to be seen for all remaining study visits, if possible.

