Fingerstick glucose values of <50 mg/dL (2.78 mmol/L) should be confirmed by laboratory plasma glucose measurements and if three or more are observed within 12 hours subsequent to administration of study drug without a reasonable explanation (such as increased physical activity and/or skipped meal), the patient will be discontinued from treatment with study drug and rescued with glucose administration (20g of glucose tablets) which will be available at all times at the study site. This information will be recorded in the patient's diary and the patient will be instructed to contact the study site if this occurs. The patient will continue to be seen for all remaining study visits. Sites will instruct patients to immediately perform a finger stick glucose measurement if any symptoms occur that may be related to hypoglycemia (e.g., weakness, dizziness, shakiness, increased sweating, palpitations, or confusion), and to avoid delay in treating these symptoms. The measurements will be recorded in the patient diary. Patients will always carry glucose tablets with them and ingest 3-4 tablets if hypoglycemia occurs.

Hypoglycemia and associated symptoms (e.g., weakness, dizziness, shakiness, increased sweating, palpitations, or confusion), have been associated with insulin administration, including ORMD-0801.

Table 1: Schedule of Assessments

Assessments	Screening	Placebo	Treatment						Un Scheduled Visit	End-of-Study / Early Termination
			0	1	2	4	8	12		
Week	up to -4	-2	0	1	2	4	8	12	Not Defined	16
Days	Up to -28	-14	7± 2	7± 2	14± 2	28± 2	56± 2	84± 2		112±2
Visit	1	2	3	4	5	6	7	8	Un Scheduled	9
Written informed consent	X									
Medical history	X									
Medication history	X	X	X	X	X	X	X	X		X
Complete physical examination	X		X					X		(X ¹)
Brief physical examination		X	X	X	X	X	X	X		
Treatment		X	X	X	X	X	X			
Medication compliance check			X	X	X	X	X	X		
ECG	X									(X ¹)
Vital signs	X	X	X	X	X	X	X	X		(X ¹)
Clinical laboratory evaluations ²	X		X			X	X	X	(X ¹)	X
Fasting blood glucose ³		X	X			X	X	X	(X ¹)	X
Fasting Insulin ³		X	X			X	X	X		X
Self-monitored fasting morning blood glucose ⁴		X	X	X	X	X	X	X		
Adiponectin			X			X	X	X		X
FibroMax Test			X					X		
Fibroscan Test			X					X		
MRI PDFF			X					X		

¹Only if investigator deems necessary

²Chemistry (electrolytes, BUN, creatinine, glucose, LFTs) and CBC

³Fasting blood glucose and insulin will be used to determine HOMA estimates.

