⁴Self-monitoring (finger-stick) of fasting blood glucose will required 3 days weekly in the morning and recorded in patient diaries.

TREATMENT REGIMEN

The treatment regimen will consist of a soft gelatin capsule containing 8 mg insulin, and 75 mg SBTI. Patients will take 2 capsules daily in the morning with or without food.

SAFETY EVALUATIONS

See complete instructions about Safety and Adverse Events evaluation and reporting in **Appendix B**.

- Adverse events will be collected throughout the study beginning from the time the patient signs the consent form until the EOS evaluations
- Concomitant medications/therapies will be recorded throughout the duration of study, beginning from the time the patient signs the informed consent.
- Vital signs (blood pressure, heart rate) will be measured in the sitting position after at least 5 minutes of rest at all visits
- Clinical laboratory evaluations (chemistry, hematology) will be performed at screening and at weeks 0, 4, 8, 12, and 16.
- Treatment of significant hyperglycemia, will be tailored to the medical history and needs of the patient, as per recommended treatment guidelines.
- Symptomatic hypoglycemia - Hypoglycemia as noted by a feeling of hypoglycaemia with concomitant blood glucose measurements below 70.
 - All occurrences of hypoglycemia will be treated with orange juice, 3-4 glucose tablets, or a 20% glucose solution via an I.V. bolus injection over 1 to 2 minutes and the subject will be monitored until symptoms have resolved.
 - If three or more finger stick glucose values of <50 mg/dL (2.78 mmol/L) are observed in one week within 12 hours subsequent to administration of study drug without a reasonable explanation (such as increased physical activity and/or skipped meal), the patient will be discontinued from treatment with study drug. This information will be recorded in the patient's diary and the patient will be instructed to contact the study site if this occurs. The patient will continue to be seen for all remaining study visits.
 - The site will instruct patients to immediately perform a finger stick glucose measurement if any symptoms occur that may be related to hypoglycemia (e.g., weakness, dizziness, shakiness, increased sweating, palpitations, or confusion), and to avoid delay in treating these symptoms. The measurements will be recorded in the patient diary.
 - Patients will always carry glucose tablets with them and ingest 3-4 tablets if hypoglycemia necessitates it.

REFERENCES

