APPENDIX B: Adverse Event Reporting

Adverse Events

Information about all adverse events, whether volunteered by the patient, recorded in the patient's diary, discovered by Investigator questioning, or detected through physical examination, laboratory test or other means, will be collected and recorded on the Adverse Event Case Report Form and followed-up as appropriate.

Medical conditions present at study entry are considered pre-existing conditions and will be documented as medical history in the study source and CRF documents. All adverse events, including worsening of pre-existing conditions, must be reported and documented as described below.

Definitions

An adverse event is any untoward medical event that occurs in a patient or patient administered a pharmaceutical product and that does not necessarily have a causal relationship with this treatment. An adverse event can therefore be any unfavorable and unintended sign (including abnormal laboratory findings), symptom, or disease temporally associated with the use of a medicinal (investigational) product, whether or not related to the medicinal (investigational) product.

Assessment of Adverse Events

Volunteered, observed, and elicited reports of adverse events must be recorded. This includes adverse events the patient reports spontaneously, those the Investigator observes, and those the study staff elicits in response to open-ended questions during study visits. Each adverse event will be assessed by the Investigator with regard to seriousness, severity, and relatedness to the study treatment for recording in the CRF.

Seriousness

International Conference on Harmonization (ICH) Guidelines define a serious adverse event (SAE) as any untoward medical occurrence that:

- Results in death.
- Is life-threatening.
- Requires or prolongs existing hospitalization.
- Results in persistent or significant disability or incapacity.
- Is a congenital anomaly or birth defect.
- Important medical events that may not result in death, be life-threatening or require hospitalization, but that may jeopardize the patient or require medical intervention to prevent one of the above outcomes, should also be considered serious when based upon the Investigator's medical judgment.

Events not to be reported as SAEs are the following:

- Routine treatment or monitoring of the studied indication, not associated with any deterioration in condition.

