Definite: The event follows a reasonable temporal sequence from the time of active study drug administration, follows a known response pattern to the drug, cannot be reasonably explained by other factors such as the patient’s condition, concomitant drugs or therapeutic interventions, AND either occurs immediately following active study drug administration, improves on stopping the study drug, or reappears on re-exposure.

Adverse Events of Hypoglycemia

The CTCAE (version 4.0) criteria for mild, moderate, and severe hypoglycemia based on blood glucose will be used, as shown below:

Mild: < 70 – 55 mg/dL (< 3.8 - 3.0 mmol/L)

Moderate: < 55 – 40 mg/dL (< 3.0 - 2.2 mmol/L)

Severe: < 40 – 30 mg/dL (< 2.2 - 1.7 mmol/L)

Life Threatening: < 30 mg/dL (< 1.7 mmol/L)

Recording Adverse Events

All adverse events experienced during the trial, regardless of relationship to study medication, must be recorded on the Adverse Event CRF from the time of patient consent until completion of patients End of Study visit (Visit 9). All serious adverse events will be collected through Visit 9. The Investigator must continue to follow all non-serious events possibly related to the study medication and all serious adverse events until they resolve or until the Investigator assesses them in writing as chronic or stable.

Regardless of relationship to study medication, the event must be recorded on the Adverse Event CRF. Adverse event documentation should include the following information:

- Standard medical terminology for the AE
- Description of adverse event
- Date and time of onset
- Date and time of resolution of the adverse event
- Whether or not the event is ongoing
- Severity of the event
- Relationship between the adverse event and the investigational product
- Description of any actions taken (e.g., medications, treatments)
- Outcome of the AE
- Whether or not the effect was serious and/or unanticipated

Whenever possible, a diagnosis should be given when signs and symptoms are due to common etiology (e.g., cough, runny nose, sneezing, sore throat, and head congestion should be reported as "upper respiratory infection"). For the purposes of this study, hypoglycemic events will be considered adverse events and should be recorded in source and CRF records.

When a diagnosis is not available, each adverse event should be reported separately. For example, "nausea and vomiting" should be split into two separate events.

Reporting Serious Adverse Events

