In accordance with Federal regulations, Investigators will be notified of the occurrence of serious, unexpected and related adverse events.

The Investigator must report all serious adverse events to Sponsor within 24 hours of the site being notified of the event. Investigators must also report these events to the Institutional Review Board (IRB) in accordance with the IRB's reporting guidelines, within the IRB specified timeframe, or no later than 48 hours after knowledge of the event.

For submission of these events to the Israeli Regulatory Agency? the Sponsor will follow FDA regulations 21 CFR 312.32. If the event is determined to meet the requirements of IND Safety Reporting then expedited reporting requirements to the FDA will be followed. The Sponsor may need to issue an Investigator notification, to inform all Investigators involved in any study with the same drug (or therapy) that this serious unexpected suspected adverse reaction (SUSAR) has occurred.

Investigator Reporting Procedures

The PI or other study personnel must immediately (within 24 hours) inform Sponsor of any AE considered serious (as defined above) or otherwise medically significant. Notification should be via facsimile transmission of a written report signed by the PI. Notification must include the PI's assessment as to whether the event was or was not related to the use of the study medication. The Sponsor contact information is as follows:

Oramed Ltd.
[name]
[name]
[name]

The Principal Investigator must also promptly inform the governing IRB of the serious adverse event per the governing IRB's requirements.

The CRO will notify Oramed within 24 hours of receipt. Any SAE that occurred within 30 days after last dose will be followed and reported as above.

Pregnancy Reporting

If the subject or partner of a subject participating in the study becomes pregnant during the study or within 30 days of discontinuing study medication, the Investigator should report the pregnancy to Oramed within 24 hours of being notified. The Exposure In Utero form to the Investigator for completion.

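### Patients who leave the study early have no scheduled contact to detect new SAEs in the 30 days after last dose, although the protocol requires such SAEs to be followed and reported

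*Protocol*

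**What the plan says.** **When leavers are assessed.** The Protocol section on End-of-Study and early discontinuations states: "Patients who are discontinued early from the study will complete the EOS evaluations at the time of early discontinuation". Table 1 puts both situations in its last column, headed "End-of-Study / Early Termination" and numbered Visit 9. No visit or call follows it.

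**When collection ends.** Safety Evaluations states: "Adverse events will be collected throughout the study beginning from the time the patient signs the consent form until the EOS evaluations". Appendix B, Recording Adverse Events, ends recording on the adverse event CRF at the End of Study visit and adds: "All serious adverse events will be collected through Visit 9".

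**The 30-day duty.** Appendix B, Investigator Reporting Procedures, states: "Any SAE that occurred within 30 days after last dose will be followed and reported as above".

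**How events come to light.** Appendix B, Assessment of Adverse Events, counts spontaneous reports, investigator observations and "those the study staff elicits in response to open-ended questions during study visits". For serious events, "The Investigator must report all serious adverse events to Sponsor within 24 hours of the site being notified of the event".

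**What limits the point.** Appendix B has the investigator follow "all serious adverse events until they resolve or until the Investigator assesses them in writing as chronic or stable". Patients taken off drug under the glucose rules are to remain on the visit schedule (Self-Monitoring section, in one place only if possible; Safety Evaluations).

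**The concern.** For a patient who leaves the study, the protocol gives two different ends to the SAE period: the exit visit, and 30 days after last dose. Active questioning stops at the first, while the duty to follow and report runs to the second.

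This matters for two reasons. Safety is the primary objective. In addition, Study Population and Size makes enrolment of a further 20 patients depend on approval after the first 10 patients' results are presented, once their 4-week follow-up is complete. A leaver among those 10 has no scheduled follow-up after exit. With 10 patients, each is 10% of the group under review (1/10), so one incompletely observed patient counts.

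**Working it through.** The protocol gives no figure of its own to reproduce. The check sets the passages side by side and adds day arithmetic.

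**Step 1: where collection ends for a leaver.** Collection runs to the EOS evaluations (Safety Evaluations). Those evaluations take place at exit (End-of-Study section). Table 1 treats early termination as Visit 9, the end of SAE collection in Appendix B. Taken together, planned collection ends at exit.

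**Step 2: what can detect a new SAE after exit.** Staff elicit events at visits, and Table 1 has none after early termination. The 24-hour reporting clock starts when the site is told. Follow-up to resolution or stability applies to events already known. What remains is a report volunteered by the patient or someone else.

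**Step 3: size of the uncovered window.** Inputs: the 30-day period (Appendix B), and *g*, the days from last dose to exit (not given, so varied).

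Uncovered days = max(0, 30 − *g*)

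| *g* (days) | Uncovered days | Share of 30 |
|---|---|---|
| 0 | 30 | 100% |
| 7 | 23 | 77% |
| 14 | 16 | 53% |
| 21 | 9 | 30% |
| 28 | 2 | 7% |
| 30 or more | 0 | 0% |

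**Step 4: the trial's own visit spacing.** Assume exit at a scheduled visit, with the last dose on or after the previous visit. Taking the week numbers of Table 1 (0, 1, 2, 4, 8, 12) as days 0, 7, 14, 28, 56 and 84, the gaps are 7, 7, 14, 28 and 28 days. The extracted table shows 7 ± 2 in the day row for Visit 3; day 0 is used here because that column is week 0. Uncovered days run from 30 − gap to 30:

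- Visits 4 and 5: 30 − 7 = 23, so 23 to 30
- Visit 6: 30 − 14 = 16, so 16 to 30
- Visits 7 and 8: 30 − 28 = 2, so 2 to 30

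With ±2 days at both ends of a gap, the lower ends fall by up to 4 days, but not below 0.

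**Step 5: completers.** Visit 8 is day 84 and Visit 9 is day 112. With the last dose on the day of Visit 8, 112 − 84 = 28 and 30 − 28 = 2 days are uncovered. With the last dose the day before, 112 − 83 = 29 and 1 day is uncovered. At the extremes of both ±2-day windows the Visit 8 to Visit 9 gap runs from 24 to 32 days, so the shortfall from a last dose at Visit 8 is 0 to 6 days.

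**The case against.** **The passages need not conflict.** No sentence says outright that SAE collection ends at exit. The body text gives Visit 9 as week 16, and the link from exit to Visit 9 rests partly on a shared column header. Recording Adverse Events can be read as governing the CRF, and the 30-day sentence as a further reporting duty that applies to every patient. Safety Evaluations refers to Appendix B for full instructions, so its short bullet need not override that duty. This stands: a reader might infer a flat contradiction that makes the two rules impossible to follow together, and the text does not support that. It does not remove the detection gap, because no contact after exit is scheduled on either reading.

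**Volunteered events count.** Appendix B accepts events from any source. A post-exit SAE known to the site goes to the Sponsor within 24 hours and to the IRB no later than 48 hours after it is known, whatever the CRF cut-off. This also stands, and it narrows the point to SAEs that nobody reports to the site.

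**The size is hypothetical.** The uncovered days depend on an assumed gap, and the earlier six-week study described in Appendix A reported no serious events. A reader might infer that SAEs will be missed. The protocol gives neither a number of leavers nor an SAE rate for this trial, so no such count can be supported.

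**Most patients are unaffected.** This is right for completers, apart from a nominal difference, and for patients stopped under the glucose rules who stay on the schedule.

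**Conclusion.** The point holds for patients who leave the study within 30 days of their last dose without completing it. For them, up to 30 days of the SAE window rely on passive notification, and the wording leaves unclear whether an SAE in that time belongs in the collected data. This rests on two assumptions: that the exit evaluations serve as the EOS evaluations for a leaver, and that exit falls soon after the last dose. If exit is 30 or more days after last dose, there is no gap.

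The point covers new SAEs only. The protocol sets no 30-day duty for non-serious events, so none is claimed. It is a cheap improvement to a safety-focused pilot, not a defect that undermines the design.

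**What to change.** Reconcile Safety Evaluations and Recording Adverse Events with the 30-day sentence in Appendix B:

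- **Early leavers, wording.** State that SAE collection and CRF recording continue to 30 days after the last dose of study drug, whatever the date of the early termination visit, or to that visit if it is later. Defining the period by last dose avoids relying on Visit 9, which has no clear date for a leaver. Say also whether run-in placebo counts as a dose for this purpose.
- **Early leavers, contact.** Add to the early discontinuation text and to Table 1 one phone contact at 30 days after last dose, for those who exit sooner and have not withdrawn consent to contact.
- **Completers.** Align the wording of the two periods; no extra call is needed.

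The cost is a wording amendment and one phone call per early leaver. Leavers who refuse contact will stay uncovered.

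### The hypoglycaemia stopping rule appears in two versions that differ in counting window, laboratory confirmation and rescue at discontinuation

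*Protocol*

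**What the plan says.** Two sections of the protocol carry the rule.

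**Self-Monitoring Fasting Blood Glucose and Patient Diaries.** "Fingerstick glucose values of <50 mg/dL (2.78 mmol/L) should be confirmed by laboratory plasma glucose measurements". The same sentence then says that a patient with three or more such values within 12 hours of study drug, and no reasonable explanation, stops study drug and is "rescued with glucose administration (20g of glucose tablets) which will be available at all times at the study site". Later in the paragraph patients are told to test at once if they have symptoms "and to avoid delay in treating these symptoms", and "Patients will always carry glucose tablets with them and ingest 3-4 tablets if hypoglycemia occurs".

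**Safety Evaluations.** Symptomatic hypoglycaemia is described as "Hypoglycemia as noted by a feeling of hypoglycaemia with concomitant blood glucose measurements below 70" (no unit printed). Beneath that, "All occurrences of hypoglycemia will be treated with orange juice, 3-4 glucose tablets, or a 20% glucose solution via an I.V. bolus injection". The stopping rule is then restated for three or more finger-stick values below 50 mg/dL that "are observed in one week within 12 hours subsequent to administration of study drug", again without a reasonable explanation. This version mentions neither laboratory confirmation nor 20 g of glucose. The instructions to test at once, not to delay treatment and to carry tablets are repeated.

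Neither section is said to take precedence over the other.

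**The concern.** A stopping rule has to give the same answer whichever page is open. Here three of its parts differ between the sections: the period over which lows are counted, whether a finger-stick value needs a laboratory result behind it, and what is given when the rule is met. Two staff members who each follow the protocol faithfully could reach opposite decisions on the same patient's diary.

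This matters more than an ordinary wording slip because safety is the primary objective, hypoglycaemia is the potential adverse event that Appendix B names for the product, and the results of the first 10 patients go to the Helsinki Committee before 20 more are enrolled. Discontinuations for low glucose are part of what that committee will see, and under the present text their number depends partly on which section was applied.

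**Working it through.** No power or sample-size calculation bears on this point. The check is a comparison of the two texts, with a little arithmetic on the rescue amounts.

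| Element | Self-monitoring section | Safety Evaluations |
|---|---|---|
| Threshold | below 50 mg/dL | below 50 mg/dL |
| Number of values | three or more | three or more |
| Window | 12 hours after study drug | one week, within 12 hours after study drug |
| Laboratory confirmation | should be obtained | not mentioned |
| Rescue when the rule is met | 20 g of tablets, available at the site | no specific step; orange juice, 3-4 tablets or IV bolus for all occurrences |
| Self-treatment of any low | 3-4 tablets, no delay | 3-4 tablets, no delay |

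**Step 1, the window.** Capsules are taken once daily in the morning. Take a patient with one unexplained value below 50 mg/dL within 12 hours of dosing on each of three days in one week. Under Safety Evaluations the count is 3 in one week, so the rule is met. Under the self-monitoring text, read as one 12-hour period after a dose, the largest count in any period is 1, so it is not met. Scheduled self-monitoring is one fasting morning reading on three days a week. It supplies at most 1 reading in any 12-hour period, so scheduled readings alone can never reach 3 under that text. At least 2 of the 3 would have to be additional readings, for example those prompted by symptoms.

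**Step 2, confirmation.** The self-monitoring sentence reads "should be confirmed by laboratory plasma glucose measurements and if three or more are observed within 12 hours subsequent to administration of study drug". It does not say whether a value without a laboratory result still counts, nor when the sample must be drawn. Readings are taken at home, and both sections tell the patient not to delay treatment. A sample drawn afterwards cannot be relied on to show the low. The documents give no figure for how often it would. By contrast, the high-glucose rule in the same section sets out a path: contact the clinic, laboratory draw, and a possible repeat within one week.

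**Step 3, rescue.** At the point of discontinuation one text names 20 g of tablets. The other leaves three options with no rule for choosing among them. Can the amounts agree? Tablet strength is not given, so solve for it:

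- 4 tablets = 20 g requires 20 / 4 = 5.0 g per tablet
- 3 tablets = 20 g requires 20 / 3 = 6.7 g per tablet

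For assumed strengths, 3 to 4 tablets give:

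- 3 g: 9 to 12 g
- 4 g: 12 to 16 g
- 5 g: 15 to 20 g
- 6 g: 18 to 24 g

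The amounts differ at 3 or 4 g and can coincide from 5.0 to 6.7 g. The documents therefore show two units without a conversion. They do not show two different amounts.

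**Step 4, the event record.** Appendix B collects adverse events from diaries as well as from laboratory tests, treats hypoglycaemic events as adverse events to be entered in source and CRF records, and grades them by blood glucose. It sets no condition of laboratory confirmation. Step 2 therefore bears on the stopping-rule count only.

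**The case against.** The strongest reply is that the two sections are layers of one scheme: every low is treated at once, and a further rescue step is added when a patient is discontinued. Much of this stands. A reader might infer from the 20 g sentence that rescue is held back until a third low. The documents do not support that, because the same paragraph tells patients to treat without delay and to take three to four tablets, as Safety Evaluations does. For a first or second low the sections agree.

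A reader might also infer that the two stated amounts conflict, perhaps by a factor of about two. That depends wholly on an assumed tablet strength, and the amounts may be meant for different situations. The absence of an IV volume is missing detail, not a contradiction.

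It can further be said that the confirmation sentence does not expressly exclude unconfirmed values. That is correct, and it is why the effect on the count is stated conditionally.

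Finally, the 12-hour phrase in the self-monitoring section might mean that each value must fall within 12 hours of some dose, with no outer limit. That does not remove the discrepancy. It reverses it: one such low in each of three separate weeks would then meet that text but not the one-week rule in Safety Evaluations. Layering explains the treatment instructions. It does not explain two counting windows for one rule.

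**Conclusion.** The point holds as a contradiction between two statements of one safety stopping rule. The window differs in a way that changes the decision for an identifiable pattern of readings. The status of an unconfirmed finger-stick value is open in one section and not raised in the other. The rescue attached to discontinuation appears in only one of them.

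Its size cannot be put as a number: the protocol gives no expected rate of values below 50 mg/dL and no rate at which laboratory samples would confirm them. The example in the working rests on reading the 12-hour phrase as a single period after one dose.

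A reader might go further and conclude that hypoglycaemia will be under-recorded as an adverse event. Appendix B does not support that. One study centre is named, so the divergence to expect is between staff members or occasions, not between sites. The rule should be put right because it governs discontinuation in a trial whose primary objective is safety. No view is taken on which version is correct.

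**What to change.** Reconcile the two sections into one text and have the other refer to it. That text should keep immediate treatment of a low apart from the stopping rule, and state once, as the responsible clinicians decide:

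- the period over which values are counted;
- whether a finger-stick value must be laboratory-confirmed to count, given that treatment is not to wait for a blood draw;
- the rescue at discontinuation, in terms that can be read against the self-treatment instruction.

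The cost is rewording of two passages and of the patient instructions. No new procedure or visit is needed.
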